6. INTRODUCTION AND STUDY RATIONALE

6.1. Unmet Medical Need

5-fluorouracil (5-FU), an anti-malignant tumor antimetabolite, was discovered by Heidelberger et al. in 1957¹. Chemotherapy regimens containing 5-FU drugs as the backbone are mainstays for the treatment of many cancers including breast, colorectal, and gastric cancer. Many combination chemotherapies employing 5-FU with chemical modulators such as leucovorin and other anti-malignant tumor agents have been investigated and have demonstrated efficacy against a variety of carcinomas to date². Oral fluoropyrimidines such as S-1, a fixed dose combination of tegafur, a prodrug of 5-FU, gimeracil, a dihydropyrimidine dehydrogenase (DPD) inhibitor that prevents degradation of 5-FU by the body and maintains 5-FU exposure, and oteracil potassium, an orotate phosphoribosyltransferase (OPRT) inhibitor that decreases the activity of 5-FU in normal gastrointestinal (GI) mucosa have been developed³. However, chemotherapies using 5-FU or S-1 can cause intrinsic and acquired resistance to the 5-FU drugs. In non-clinical models, overexpression of deoxyuridine triphosphatase (dUTPase) reduced the sensitivity of cancer cells to 2'-deoxy-5-fluorouridine (FdUrd) by fourfold–fivefold⁴ and transient suppression of dUTPase sensitized cancer cells to FdUrd with the intracellular accumulation of deoxyuridine triphosphate (dUTP).⁵ In clinical studies in patients with colorectal cancer (CRC), dUTPase expression in the tumor tissue appeared to correlate with poor prognosis and overall survival (OS) outcomes as well as resistance to 5-FU-based chemotherapy⁶. These observations indicate that dUTPase may be one of the causal factors for resistance to 5-FU-based chemotherapies. Therefore, the development of new drugs that can be expected to achieve higher efficacy than the existing 5-FU drugs is urgently required.

Non-small cell lung cancer (NSCLC) remains the leading cause of cancer-related mortality worldwide⁷. Despite treatment with immunotherapy, platinum- and taxane-based chemotherapy, patients with refractory metastatic NSCLC have a median survival of approximately 8 to 10 months. Despite the increased number of treatment options available for patients with NSCLC, there has been little OS improvement from several new agents, including pemetrexed, erlotinib and bevacizumab beyond very small subpopulations. Overall, this group of patients only has an OS of about 8 months after progression from platinum agents. Once resistance to tyrosine kinase inhibitors (TKIs) occurs, the patients who have epidermal growth factor receptor (EGFR) mutations or anaplastic lymphoma kinase or ROS translocations will have a rapid disease progression.⁸ Therefore, the majority of NSCLC cases remain a disease with high burden and unmet medical need.

6.2. TAS-114

TAS-114 is a modulator of 5-FU. TAS-114 potently inhibits the conversion of 2'-deoxyuridine-5'-triphosphate (dUTP; FdUTP) into 2'-deoxyuridine-5'-monophosphate (dUMP; FdUMP) by the reversible inhibition of dUTPase which acts as a gatekeeper protein for uracil and 5-FU misincorporation into DNA.

TAS-114 itself does not have an antitumor effect. TAS-114 can enhance antitumor activity of 5-FU. [Section 6.4.1](#) describes the mechanism of action when TAS-114 is used in combination with 5-FU.

6.2.1. ADME and Toxicological Profiles of TAS-114

The pharmacokinetics (PK) of TAS-114 were evaluated in the Japanese healthy volunteers, and the plasma protein binding and metabolism of TAS-114 have been studied in non-clinical studies.

6.2.1.1. Absorption

The absorption of TAS-114 was increased dose-proportionality in healthy human volunteers under the fasting condition at dose ranges from 6 mg to 300 mg. The average of time to maximum plasma concentration (t_{max}) and elimination half-life ($t_{1/2}$) were 1.00 hour to 2.00 hours and 1.49 hour to 3.38 hours, respectively, and multiple administration of TAS-114 at 60 mg and 150 mg did not give any effects on the PK of TAS-114. Although the mean plasma concentrations of TAS-114 were increased by food at a dose of 60 mg, there was no significant food effect on TAS-114 absorption.

6.2.1.2. Distribution

The plasma protein binding ratios of TAS-114 were 78.1 to 81.5% in humans.⁹

Metabolism

Cytochrome P-450 (CYP) isozymes involved in the metabolism of TAS-114 were investigated using human hepatic microsomes in which various CYP isozymes were expressed.¹⁰ The results have shown that M-1, a primary metabolite of TAS-114, is produced specifically by CYP3A4.

6.2.1.3. Excretion

In humans, the urinary excretion of TAS-114 was only 1.28% to 5.56% of dose, suggesting that the urinary excretion of TAS-114 was a minor pathway of TAS-114 elimination. Based on the mass balance study of animals,¹¹ the major elimination pathway of TAS-114 was considered to be metabolism and subsequent biliary excretion of TAS-114 metabolites.

6.2.1.4. Drug Interactions

In 2 drug interaction studies, the inhibitory effect of TAS-114 on various CYP isozymes was examined using human hepatic microsomes. The results showed that TAS-114 exhibited the most potent inhibitory effect on CYP2C9 (50% inhibitory concentration [IC50 value] = 57.7 μ mol/L), and the IC50 values for TAS-114 on the CYP isozymes other than CYP2C9 were 100 μ mol/L or higher.

Enzyme induction for CYP isozymes by TAS-114 (including CYP3A4) was investigated using cryopreserved human hepatocytes during which enzyme induction (auto induction) for CYP3A4 by TAS-114 was observed. However, in a Phase 1 clinical study in healthy volunteers, the plasma concentration of TAS-114 and the urinary excretion of cortisol and 6 β -hydroxycortisol suggested that although enzyme induction of CYP3A4 occurred after multiple administration of TAS-114 at 150 mg/body/dose twice daily (BID), the extent of auto induction was minimal. TAS-114 did not induce other CYP isozymes, such as CYP1A2. An in vitro study using human liver S9 fraction showed that TAS-114 has the potential to inhibit DPD, an enzyme responsible for 5-FU degradation.

6.2.1.5. Toxicology

No effect of TAS-114 on the central nervous system or respiratory system was observed after single-dose oral administration at doses up to 1000 mg/kg in rats. In studies of the cardiovascular system, TAS-114 suppressed the human ether-a-go-go related gene current at doses of 10 $\mu\text{mol/L}$ or higher in vitro (a concentration about 6 times higher than the mean maximum observed plasma concentration (C_{max}) value in human subjects administered 300 mg/body TAS-114); however, in conscious dogs, no effect was observed after single-dose oral administration at doses up to 500 mg/kg.

Multiple dose toxicity was examined in rats and dogs including 4-week oral toxicity studies.^{12,13,14} The observed significant toxicities included: a prolongation of prothrombin time or activated partial thromboplastin time, slight vacuolation in the hepatocytes, decreased body weights, decreases in white blood cell (WBC) and erythrocyte counts, and atrophic changes in the lymphatic and hematopoietic tissues. No observed adverse effect levels were determined to be 200 mg/kg/day in rats and 10 mg/kg/day in dogs based on the 4-week repeated oral dose toxicity studies.

6.3. S-1

In an S-1 Phase 2 study for 2nd line NSCLC, a total of 57 patients with advanced NSCLC received S-1 30 mg/m² of S-1 every 12 hours for 14 days followed by a 7-day recovery period repeated every 3 weeks until death, progression of disease, occurrence of intolerable side effects, withdrawal of consent, or removal by Investigator. The following conclusions can be drawn:

- Although the study did not meet the criteria for progressing to Stage 3, S-1 showed antitumor activity in NSCLC, achieving a best overall confirmed response rate of 7.1%.
- Median progression-free survival (PFS) (2.9 months) and OS were comparable to those observed with pemetrexed and docetaxel when used as 2nd-line treatment for patients with NSCLC.

- S-1 30 mg/m², administered orally BID from Days 1 through 14, with a recovery period on Days 15 through 21, demonstrated a safety profile consistent with previous reports of S-1.¹⁶

S-1 is approved in Japan for the treatment of NSCLC. However, whilst S-1 is approved in the European Union and a number of other Asian countries for the treatment of a number of other advanced cancers, it is not approved for the treatment of NSCLC elsewhere in the world. In addition, S-1 is not approved in the United States (US). As of January 24, 2016, over 1.7 million patients have been treated with S-1 in the post-authorization setting since first approval in 1999.

6.4. TAS-114/S-1

CCI

CCI

CCI

CCI

6.5. Study Rationale

CCI

CCI

The summary of PK parameters is presented in [Table 4](#) (European study) and [Table 5](#) (Japanese study). CCI

CCI

6.6. Rationale for Selection of TAS-114 and S-1 Doses and Schedules

CCI

6.6.2. Rationale for S-1 Dose Selection

Two previous Phase 1 studies with S-1 monotherapy have been conducted. In the first study, conducted in the US¹⁷, the MTD for S-1 was established as 30 mg/m² administered orally BID in a fasting condition. In the second study, conducted by the European Organisation for Research and Treatment of Cancer¹⁸ the MTD for S-1 was established as 40 mg/m² administered orally BID in a fasting condition although the MTD was found out to be intolerable because of GI toxicities in the Phase 2 trial.

CCI

CCI

6.6.3. TAS-114/S-1 Dose Selection for Phase 2 Study

In conclusion, the dose of TAS-114/S-1 to be used in this Phase 2 (TO-TAS-114-201), to be conducted in Europe, Japan, and US, was determined to be 400 mg/30 mg/m² BID.

7. STUDY OBJECTIVES

7.1. Primary

- To compare PFS of patients with advanced or metastatic NSCLC, when treated with TAS-114/S-1 combination versus S-1.

7.2. Secondary

- To investigate the OS, overall response rate (ORR), disease control rate (DCR), and duration of response (DR)
- To investigate the safety and tolerability.

CCI

8. INVESTIGATIONAL PLAN

8.1. Study Design

This is a randomized, open-label, Phase 2 study of TAS-114 administered in combination with S-1, to investigate the efficacy, safety, and tolerability of the TAS-114/S-1 regimen in patients with advanced or metastatic NSCLC.

[figure not shown]
The study will be conducted internationally in 2 regions: Asian (Japan) and Western (Europe and US). Patients will be randomized to TAS-114/S-1 arm versus S-1 control arm in a 1:1 ratio.

Randomization will take place once the consented patient has completed all the necessary baseline procedures and is deemed eligible for study entry. Treatment assignment will be done centrally using a dynamic allocation method (biased coin) via an interactive voice/web response system (IXRS) stratified by:

- Geographical region (Region 1: Asian [Japan]; Region 2: Western [Europe and US])
- Histological subtypes (nonsquamous cell carcinoma [including mixed] and squamous cell carcinoma)

The overall study design is described in [Figure 3](#).

Figure 3: Study Schema

Stratification factors:

1. Geographical: Region 1: Asian (Japan); Region 2: Western (Europe and US)
2. Histological subtypes: non-squamous (including mixed); squamous

R = Randomization

8.1.1. Study Duration

Patients will receive the study drug according to the proposed treatment schedule until progressive disease (PD), occurrence of intolerable side effects, removal by the Investigator, or withdrawal of consent. A patient is considered discontinued from study treatment when either TAS-114/S-1 or S-1 alone is discontinued.

For the purpose of the final analyses, the study will be considered completed when all patients have discontinued from treatment or a minimum of 12 months from the date of the first day of treatment with TAS-114/S-1 or S-1 of the last patient enrolled or until the target number of

events (deaths, n=80) is reached, whichever occurs last. This analysis may still be done even if there are patients still on treatment.

8.2. Study Population

The study population will include male and female patients age 18 years or older (20 and older in Japan) with histologically or cytologically confirmed advanced or metastatic NSCLC for whom standard therapy no longer exists, based on local guidelines and practices, and according to the following inclusion and exclusion criteria.

8.2.1. Inclusion Criteria

A patient must meet all of the following inclusion criteria to be eligible for enrollment in this study:

1. Provision of written informed consent consistent with International Council for Harmonisation (ICH)-Good Clinical Practice (GCP) guidelines, and respective local law;
2. Age \geq 18 years old (\geq 20 years old in Japan);
3. Histologically diagnosed or cytologically proven advanced or metastatic NSCLC patients, either Stage IIIB/Stage IV disease (according to Version 7 of the International Association for the Study of Lung Cancer Staging Manual in Thoracic Oncology²⁰), or recurrent disease following radiation therapy or surgical resection;
4. Patients who had received at least 2 prior therapies for advanced or metastatic disease condition, including platinum doublet and pemetrexed, docetaxel, or immunotherapy and were refractory to or unable to tolerate their last prior therapy. For patients with known EGFR activating mutations or anaplastic lymphoma kinase translocations and/or ROS1 rearrangements, appropriate targeted treatment should have been used. The following histological tumor types are also eligible to be included:
 - Adenocarcinoma with bronchiolo-alveolar differentiation
 - Large cell carcinoma
5. Tumor is locally advanced or metastatic and not suitable for surgery and radiotherapy is not indicated;
6. Measurable disease as defined by Response Evaluation Criteria in Solid Tumors (RECIST) criteria (Version 1.1, 2009)²⁰;
7. Eastern Cooperative Oncology Group (ECOG) performance status 0 or 1 (see Appendix A);
8. Predicted life expectancy of at least 3 months;
9. Able to take medications orally;
10. Adequate organ function as defined by:
 - a. Adequate bone marrow function: absolute neutrophil count (ANC) \geq 1500/mm³, hemoglobin \geq 10.0 g/dL, platelets \geq 100,000/mm³
 - b. Adequate liver function: Total bilirubin \leq 1.5 \times upper limit of normal (ULN), ALT/AST \leq 3 \times ULN (existent liver metastases \leq 5 \times ULN)

- c. Adequate renal function: Calculated creatinine clearance ≥ 50 mL/min (Cockcroft-Gault Equation)
11. Women of childbearing potential (WOCBP) must have a negative pregnancy test (urine or serum) within 7 days prior to starting the study drug. Both males and females must agree to use effective birth control during the study (prior to the first dose and for 6 months after the last dose) if conception is possible during this interval. Female patients are considered to not be of childbearing potential if they have a history of hysterectomy, or are postmenopausal defined as no menses for 12 months without an alternative medical cause. For both males and females, see [Section 8.7.2](#) for definitions of contraceptive methods considered effective for this protocol;
12. Willing and able to comply with required scheduled visits and study procedures.

8.2.2. Exclusion Criteria

A patient will be excluded from this study if any of the following criteria are met:

1. Treatment with any of the following within the specified time frame prior to study drug administration:
 - Major surgery within prior 4 weeks and minor surgery within 7 days;
 - Radiotherapy for extended field within prior 4 weeks or limited field within prior 2 weeks;
 - Any anticancer therapy or investigational agent within prior 3 weeks.
2. A serious illness or medical condition including but not limited to the following:
 - Patients with brain or subdural metastases are not eligible unless they have completed local therapy and have discontinued the use of therapeutic corticosteroids and are stable for at least 1 month before study drug administration;
 - Known leptomeningeal metastatic disease;
 - Known acute or chronic active systemic infection;
 - Any cardiac disease, such as myocardial infarction, unstable angina, symptomatic congestive heart failure (CHF) New York Heart Association (NYHA) class III or IV (see Appendix B) within the last 6 months. If > 6 months, cardiac function must be within normal limits and the patient must be free of cardiac-related symptoms;
 - Chronic nausea, vomiting, or diarrhea considered to be clinically significant by investigator's discretion;
 - Current or past severe lung disease (eg, interstitial pneumonia, pulmonary fibrosis, or severe emphysema);
 - Pleural, peritoneal, or pericardial effusion which will require surgical intervention in the near term;
 - Any history or presence of poorly controlled GI disorders that could affect the absorption of the trial drug (eg, Crohn's disease, ulcerative colitis);

- Known human immunodeficiency virus (HIV) or acquired immune deficiency syndrome-related illness (AIDS), or chronic or acute hepatitis B or C;
 - Any other clinically significant acute or chronic medical or psychiatric condition or any laboratory abnormality that may increase the risk associated with study drug administration, or may interfere with the interpretation of study results;
 - Poorly controlled (despite medication) or severe diabetes mellitus;
 - Continuous systemic steroid administration (oral or intravenous);
 - Other concurrent active cancer (synchronous double cancer or heterochronous double cancer with a disease-free interval of 3 years or shorter, excluding lesions consistent with intraepithelial cancer, ie, carcinoma in situ, or intramucosal cancer) that is assessed as cured by local treatment.
3. Concomitant treatment with the following drugs that may interact with S-1:
- Sorivudine, brivudine, uracil, eniluracil, folinate/folinic acid, (enhance S-1 activity);
 - Cimetidine, dipyridamole, and nitroimidazoles, including metronidazole and misonidazole (may enhance S-1 activity);
 - Methotrexate (may enhance S-1 activity);
 - Clozapine (may increase risk and severity of hematologic toxicity with S-1);
 - Allopurinol (may diminish S-1 activity);
 - Phenytoin (S-1 may enhance phenytoin activity);
 - Flucytosine, a fluorinated pyrimidine antifungal agent (may enhance S-1 activity);
 - Coumarin-derivative anticoagulant (S-1 may enhance activity of coumarin-derivative anticoagulant).
4. Known hypersensitivity to S-1 or its metabolites (eg, 5-FU);
5. Patients with rare hereditary problems of galactose intolerance, Lapp lactase deficiency, or glucose/galactose malabsorption since S-1 contains lactose.
6. Previous use of TAS-114, S-1, and 5-FU drugs;
7. A pregnant or lactating female or possibly pregnant women, or men or women wishing to have children during the study period.
8. A judgment of the investigator that the patient is inappropriate for study participation.

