8.4. Patient Numbering and Treatment Allocation

All patients will sign an informed consent form (ICF) and be assigned a unique patient number. The patient numbering process is defined in the Case Report Form Completion Manual.

Investigative sites must complete all relevant eCRFs for all enrolled patients, even if the patient is not treated with study drug.

Randomization will take place once the consented patient has completed all the necessary baseline procedures and is deemed eligible for study entry. Treatment assignment will be done centrally using a dynamic allocation method (biased coin) via an IXRS stratified by:

- Geographical region (Region 1: Asian [Japan]; Region 2: Western [Europe and US])
- Histological subtype (nonsquamous cell carcinoma [including mix] and squamous cell carcinoma).

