Co-administration of other fluoropyrimidines such as capecitabine, 5-FU, tegafur, or flucytosine can lead to additive toxicities, and is contraindicated. A minimum washout period of 7 days is recommended between administration of S-1 and other fluoropyrimidines.

Sorivudine and brivudine

Sorivudine or its chemically-related analogues such as brivudine irreversibly inhibit DPD, resulting in a significant increase in 5-FU exposure. This may lead to increased clinically significant fluoropyrimidine-related toxicities with potentially fatal outcomes. S-1 must not be used with sorivudine or brivudine or within 4 weeks of the last dose of sorivudine or brivudine.

CYP2A6 inhibitors

As CYP2A6 is the major enzyme responsible for the conversion of tegafur to 5-FU, co-administration of a known CYP2A6 inhibitor and S-1 should be avoided as effectiveness of S-1 could be decreased.

Folate/folinic acid

Metabolites of folinate/folinic acid will form a ternary structure with thymidylate synthase (TS) and FdUMP, potentially increasing the cytotoxicity of 5-FU. Caution is advised as folinic acid is known to enhance the activity of 5-FU.

Nitroimidazoles, including metronidazole and misonidazole

No data are available on the concomitant use of nitromidazoles with S-1. However, nitromidazoles may reduce clearance of 5-FU and thus increase plasma levels of 5-FU. Caution is advised as co-administration may increase the toxicity of S-1.

Methotrexate

No data are available on the concomitant use of methotrexate with S-1. However, polyglutamated methotrexate inhibits thymidylate synthase and dihydrofolate reductase, potentially increasing cytotoxicity of 5-FU. Caution is advised as co-administration may increase the toxicity of S-1.

Clozapine

No data are available on the concomitant use of clozapine with S-1. However, due to possible additive pharmacodynamic effects (myelotoxicity), caution is advised as co-administration may increase the risk and severity of haematologic toxicity of S-1.

Cimetidine

No data are available on the concomitant use of cimetidine with S-1. However, co-administration may decrease clearance and, thus increase plasma levels of 5-FU. Caution is advised as co-administration may increase the toxicity of S-1.

Coumarin-derivative anticoagulant

The activity of a coumarin-derivative anticoagulant was enhanced by S-1. Caution is advised as co-administration of S-1 and coumarin anticoagulation therapy may increase the risk of bleeding.

Phenytoin

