10.2.1.1. Cycle 1, Day 1 Predose

The following assessments and procedures should be completed:

- Review Inclusion and Exclusion Criteria to ensure continued eligibility for the trial.
- Record Baseline signs and symptoms.
- Physical exam
- Record ECOG Performance status (see [Section 11.5](#))
- Record current and concomitant medications.
- Dispense TAS-114/S-1 or S-1 alone for Cycle 1.

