11. STUDY PROCEDURES

The study assessments are described by procedure in the following sections. All information required by the protocol must be recorded.

The study schedule must be followed; however, in unavoidable circumstances (eg, holidays, weekends) a window of ± 3 days is allowable for study procedures as long as the proper order of procedures and assessments is maintained. A window of ± 7 days is allowable for CT scans and follow-up visits. These windows are not applicable during the Baseline Period. If any baseline assessments are repeated on Day 1 of Cycle 1, the site must ensure the patient meets the eligibility criteria listed in [Section 8.2.1](#) and [Section 8.2.2](#) before administration of the first dose of TAS-114.

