11.2. Medical History

A complete medical history will be obtained during baseline within 28 days before first TAS-114/S-1 or S-1 control administration on Day 1 of Cycle 1.

Existing signs and symptoms will be obtained within 7 days before TAS-114/S-1 or S-1 control administration on Day 1 of Cycle 1. Those pre-existing signs and symptoms and conditions are appropriately recorded in a respective medical history page.

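### Exclusion 3 leaves out the 4-week interval after sorivudine or brivudine that Section 8.7.1 requires before S-1 (minor, cheap to correct)

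*Protocol*

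**What the plan says.** **Eligibility.** Exclusion 3 (Protocol Section 8.2.2, same wording in the synopsis) excludes "Concomitant treatment with the following drugs that may interact with S-1". Sorivudine and brivudine head the list. No period before study drug is given. Section 8.6 lists both drugs as prohibited, also without a look-back.

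**Dosing.** Section 8.7.1 explains that the two drugs irreversibly inhibit DPD and raise 5-FU exposure, and adds: "This may lead to increased clinically significant fluoropyrimidine-related toxicities with potentially fatal outcomes". It then sets the rule: "S-1 must not be used with sorivudine or brivudine or within 4 weeks of the last dose of sorivudine or brivudine".

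**When eligibility is checked.** Section 8.4: "Randomization will take place once the consented patient has completed all the necessary baseline procedures and is deemed eligible for study entry". The screening visit (Section 10.1.1) has the site record the inclusion and exclusion criteria. The predose list for Cycle 1 Day 1 (Section 10.2.1.1) says: "Review Inclusion and Exclusion Criteria to ensure continued eligibility for the trial". Section 11 adds that "the site must ensure the patient meets the eligibility criteria listed in" Sections 8.2.1 and 8.2.2, but only where baseline assessments are repeated on Day 1 of Cycle 1.

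**What is asked about earlier drugs.** Section 11.2: "A complete medical history will be obtained during baseline". Current and concomitant medications are recorded at screening, baseline and Day 1 (Sections 10.1.1, 10.1.2 and 10.2.1.1). Section 11.10 starts medication collection at signature of the consent form.

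**The concern.** The protocol holds a mandatory waiting period for two drugs, but the period is stated only in the text on concomitant medication and not in the criteria that decide entry. A site that applies exclusion 3 as written would accept a patient who finished a course of brivudine a week ago, and that patient may not yet take the drug of either arm.

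There are three possible outcomes:

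- The course is found at the eligibility check. The site plans Day 1 for after the interval, and nothing is lost.
- The course is found after randomization. PFS is counted from the day of randomization (Section 14.1.2.1.1), so the clock runs while S-1 is withheld. Baseline tests may go out of window, and the patient cannot be replaced (Section 8.5).
- The course is missed. The patient is exposed to an interaction that the protocol itself describes as possibly fatal.

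**Working it through.** The plan gives no figure to reproduce. The check compares the texts and then works out what happens to an affected patient.

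**Step 1. Does exclusion 3 reach a drug already stopped?** Exclusion 1 shows how this protocol writes a washout: it opens by referring to a time frame before study drug and then lists periods in days or weeks. Exclusion 3 has nothing of the kind. SAP Section 6.3.10 counts a drug begun before the first dose as concomitant only if it continued during study treatment. That is an analysis definition and not an eligibility rule, but it points the same way: a drug stopped before Day 1 is not concomitant.

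**Step 2. Does another criterion supply the interval?**

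| Provision | Why it does not |
|---|---|
| Exclusion 1 | Its 3-week look-back covers anticancer therapy and investigational agents only |
| Exclusion 2, general clause | Covers a medical or psychiatric condition or a "laboratory abnormality that may increase the risk associated with study drug administration", not a recent course of a drug |
| Exclusion 8 | Investigator's judgment; names no drug and no interval |
| Section 8.6 | Names both drugs, without a look-back |

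No criterion carries the 4 weeks.

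**Step 3. Who falls in the gap?** 4 weeks × 7 = 28 days. Let d be the days from the last dose of sorivudine or brivudine to planned Day 1. For d = 1 to 27 the patient meets exclusion 3 as written but is inside the Section 8.7.1 interval. Day 28 is a boundary case and is left out.

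**Step 4. What follows if the course is found only after randomization?** Assume that dosing starts on the first permitted day. The hold is h = 28 − d.

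| d (days) | h (days) |
|---|---|
| 1 | 27 |
| 7 | 21 |
| 14 | 14 |
| 21 | 7 |
| 27 | 1 |

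- *Baseline laboratory tests*: limit of 7 days before first dose (Sections 11.7.1 and 11.7.2). A sample taken j days before planned Day 1, with j from 1 to 7, is j + 28 − d days old at first dose. It stays in window only if j + 28 − d ≤ 7, that is j ≤ d − 21. For d ≤ 21 no j ≥ 1 qualifies, so every such sample expires.
- *Baseline CT*: limit of 28 days (Section 11.12). A scan taken k days before planned Day 1 is k + 28 − d days old. It stays in window only if k ≤ d, so it expires if it was taken before the last dose of the interacting drug. Example: d = 7 and k = 14 give 14 + 21 = 35 days, which is out of window.

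These are consequences for one affected patient. They say nothing about how many such patients there would be.

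**The case against.** The strongest reply is that the protocol already deals with this. Section 8.7.1 is mandatory and protects both arms. Exclusion 3 governs entry and Section 8.7.1 governs dosing, and a site can obey both. A temporary hold need not be an entry criterion, and an investigator who knows of the course can defer the patient or use exclusion 8.

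Most of this stands, and it rules out several stronger readings that a reader might infer:

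- *That the protocol permits S-1 inside the 4 weeks.* It does not. Such dosing would breach Section 8.7.1.
- *That sites are never prompted about these drugs.* They are. The criteria are recorded at screening and reviewed on Day 1, and exclusion 3 names both drugs. Only the interval is absent.
- *That a course stopped before consent cannot be recorded.* SAP Section 6.1 shows that the Concomitant Medications and Therapies form can hold prior medication, although it sets no look-back. For a patient who consents near Day −28, collection covers almost the whole interval, and a full medical history is taken as well.
- *That Section 11 always sends the site back to Sections 8.2.1 and 8.2.2.* That sentence applies only when baseline assessments are repeated on Day 1.
- *That holds and expired tests would be usual.* They arise only if the course is found after randomization, and expired tests can be repeated.

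What the reply does not remove is the mismatch. Sites decide entry from the criteria, and the criterion for these drugs lacks the interval that the protocol itself makes mandatory.

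**Conclusion.** The point holds as a minor inconsistency between eligibility and dosing rules. As written, a patient who stopped sorivudine or brivudine 1 to 27 days before planned Day 1 can be randomized although S-1 must be withheld. The size is a hold of 1 to 27 days for an affected patient whose course comes to light only after randomization, and a safety risk if it is missed altogether.

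This rests on reading concomitant as not reaching back before Day 1, which the contrast with exclusion 1 and the SAP definition support. The number of patients affected is unknown and probably small. The documents offer no basis for claiming an effect on power or bias, and the rule would touch both arms alike. What justifies a change is the stated severity of the interaction set against a correction that costs almost nothing.

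**What to change.** In exclusion 3 (Section 8.2.2) and its synopsis copy, for sorivudine and brivudine only, add: *or within 4 weeks before the first dose of study drug*. The other drugs on the list should stay as they are, because Section 8.7.1 attaches no such interval to them. At the eligibility check before randomization, have the site ask whether the patient took either drug in the 4 weeks before planned Day 1. A matching note in Section 8.6 is optional.

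The cost is one clause in two places and one question, with no new test or visit. The downside is that a very few patients start later or do not enter.
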